#### 8. QC plans

All data will be double checked on the paper CRF by the receiving EC before upload into datbase. Data queries will be referred back to the originating hospital. Data will also be double checked as it is entered from the paper CRF onto the electronic data management system. Any further data queries generated upon data entry will be referred back to the originating hospital. Records of all data queries and responses will be held by the EC.

# Appendix 1. Variable description table

Item	Data Item	Definition	Analysis type	Time window
Number		of variable		
	Study ID			
1. Patient	Demographics	1	Γ	
1.1	Age of patient at time of sample	Continuous	Univariate/multivariate	Patient admission when the sample was taken
1.2	Gender of patient	Binary	Univariate/multivariate	Patient admission when the sample was taken
1.3	Date of sample in COMBACTE	N/A		
1.4	Location of the patient at time of sample	Categorical	Univariate/multivariate	Patient admission when the sample was taken
2. Admissi	on History	1	1	
2.1	If the sample was taken as a hospital inpatient Reason for admission	Categorical	Univariate/multivariate	Patient admission when the sample was taken
2.1.1	Date of admission	Number of days between admission and index sample is Continuous	Univariate/multivariate	Patient admission when the sample was taken
2.1.2	Admitting specialty	Categorical Patient admission when the sample was taken	Univariate/multivariate	Patient admission when the sample was taken
2.2	Did the patient move wards during their admission	Categorical	Univariate/multivariate	Patient admission when the sample was taken
2.2.1	If yes, please complete the table	Number of days between admission and movement is	Univariate/multivariate	Patient admission when the sample was taken

		Continuous		
2.3	If the sample was taken as a hospital inpatient Where was patient	Categorical	Univariate/multivariate	Patient admission when the sample was taken
	admitted from			
2.4	If the sample was taken as a hospital inpatient Where was the patient discharged to	Categorical	Univariate/multivariate	Patient admission when the sample was taken
2.5	If the sample was taken in the community patient Reason for GP appointment	Categorical	Univariate/multivariate	Patient admission when the sample was taken
2.6	Did the patient have contact with a healthcare facility 6 months prior to the sample being taken?	Binary	Univariate/multivariate	Up to 6 months previous to sample
2.6.1	If yes and the visit was >24 hours, please complete the table below	Categorical	Univariate/multivariate	Up to 6 months previous to sample
2.6.2	If yes, because the patient had regular outpatient appointments, please complete the table below Frequency of visits - nature of visits	Categorical	Univariate/multivariate	Up to 6 months previous to sample
2.7	Did the patient receive any supportive measures/domestic help by friends or relatives during the presence of CDI?	Binary	Univariate/multivariate	Patient admission when the sample was taken

2.7.1	If yes, how many hours per day?	Continuous	Univariate/multivariate	Patient admission when the sample
				was taken
2.8	Did the patient receive any supportive measures/domestic help by professionals during the presence of CDI?	Binary	Univariate/multivariate	Patient admission when the sample was taken
2.8.1	If yes, how many hours per day?	Continuous	Univariate/multivariate	Patient admission when the sample was taken
2.9	Were any CDI related purchases necessary?	Binary	Univariate/multivariate	Patient admission when the sample was taken
2.9.1	If yes, please describe below	Categorical	Univariate/multivariate	Patient admission when the sample was taken
3. Laborat	ory Testing	1	1	
3.1	Did the patient have any test for other enteric pathogens up to 7 days before or up to 7 days after the EUCLID sample was taken	Binary	Univariate/multivariate	Patient admission when the sample was taken
3.1.1	If yes please indicate test results	Categorical	Univariate/multivariate	Patient admission when the sample was taken
3.2	What was the local policy for repeat testing of patients with CDI (at the time of the sample)	Binary (repeat or not repeat)	Univariate/multivariate	Patient admission when the sample was taken
4. CDI Test	ting	ſ	ſ	
4.1	Was the patient tested for CDI due to diarrhoea in the 6 months before the index sample	Binary	Univariate	Up to 6 months previous to the sample
4.1.1	If yes, date of sample and result of tests	Number of days between sample and	Univariate	Up to 6 months previous to the sample

		test is		
		Continuous		
		Decult of		
		Result of		
		Catagorical		
12	Did the nationt	Rinary	Univariato	Up to 6 months
4.2	have a diarrhoea	binary	Univariate	after the sample
	enisode in the 6			arter the sumple
	months following			
	the index sample			
4.3	Was the patient	Binary	Univariate	Up to 6 months
	tested for CDI in the	,		after the sample
	6 months following			
	the index sample			
4.3.1	If yes, date of	Number of	Univariate	Up to 6 months
	sample and result	days		after the sample
	of tests	between		
		sample and		
		test is		
		Continuous		
		Result of		
		test is		
		Categorical		
4.4	Was the Clostridium	Binary	Univariate	Patient admission
	difficile sent for	,		when the sample
	ribotyping?			was taken
4.5	Was the severity of	Binary	Univariate	Patient admission
	CDI graded?			when the sample
				was taken
4.5.1	If yes, please record	Categorical	Univariate/multivariate	Patient admission
	the severity of CDI			when the sample
				was taken
4.6	Has the patient	Binary	Univariate	Patient admission
	ever had CDI			when the sample
E Clinica	Information			was taken
5.1	Temperature	Continuous	Univariate	Patient admission
5.1	(highest reading +/-	Continuous		when the sample
	3 days of the index			was taken
	sample)			
5.2	Serum creatinine	Continuous	Univariate	Patient admission
	(highest reading +/-			when the sample
	3 days of the index			was taken
	sample)			
5.3	White cell count	Continuous	Univariate	Patient admission

	(highest +/-3 days			when the sample
	of the index			was taken
	sample)			
5.4	Serum Albumin	Continuous	Univariate	Patient admission
	(lowest +/-3 days of			when the sample
	the index sample)			was taken
5.5	Primary diagnoses	Categorical	Univariate	Patient admission
	at time of index			when the sample
	sample			was taken
5.6	Does the patient	Binary	Univariate	Patient admission
	have any significant			when the sample
	illnesses			was taken
5.6.1	If yes, are the	Categorical	Univariate	Patient admission
	illnesses:			when the sample
				was taken
	Acute/chronic			
5.6.2	Please provide	Categorical	Univariate	Patient admission
	details of the			when the sample
	significant illness			was taken
5.7	Co-morbidities		All of these could be	
			Covariates	
	Myocardial	Binary	Univariate/multivariate	Patient admission
	infarction			when the sample
				was taken
	Congestive heart	Binary	Univariate/multivariate	Patient admission
	failure			when the sample
	De debe velo e e de c	D'		was taken
	Peripheral vascular	Binary	Univariate/multivariate	Patient admission
	uisease			when the sample
	Corobrovascular	Pipany	Univariato (multivariato	Rationt admission
	disease	Billary	Onivariate/multivariate	when the sample
	uiscase			was taken
	Dementia	Binary	Univariate/multivariate	Patient admission
	Dementia	Dinary		when the sample
				was taken
	COPD	Binary	Univariate/multivariate	Patient admission
		,	,	when the sample
				was taken
	Peptic Ulcer disease	Binary	Univariate/multivariate	Patient admission
				when the sample
				was taken
	Cystic fibrosis	Binary	Univariate/multivariate	Patient admission
				when the sample
				was taken
	Diabetes without	Binary	Univariate/multivariate	Patient admission
	organ damage			when the sample

			was taken
Leukaemia within	Binary	Univariate/multivariate	Patient admission
last 5 years			when the sample
			was taken
Solid tumour within	Binary	Univariate/multivariate	Patient admission
last 5 years			when the sample
			was taken
Any other	Binary	Univariate/multivariate	Patient admission
malignancy within			when the sample
last 5 years			was taken
AIDS (not just HIV	Binary	Univariate/multivariate	Patient admission
positive)			when the sample
			was taken
Pneumonia	Binary	Univariate/multivariate	Patient admission
			when the sample
			was taken
Cardiac arrest	Binary	Univariate/multivariate	Patient admission
within 7 days of			when the sample
sample			was taken
Date of cardiac	Number of	Univariate/multivariate	Patient admission
arrest	days		when the sample
	between		was taken
	cardiac		
	arrest and		
	sample is		
	Continuous		
HIV positive	Binary	Univariate/multivariate	Patient admission
			when the sample
			was taken
Hemiplegia	Binary	Univariate/multivariate	Patient admission
			when the sample
			was taken
Mental	Binary	Univariate/multivariate	Patient admission
disorientation			when the sample
 			was taken
Connective tissue	Binary	Univariate/multivariate	Patient admission
disease			when the sample
			was taken
Mild liver disease	Binary	Univariate/multivariate	Patient admission
			when the sample
			was taken
Diabetes with organ	Binary	Univariate/multivariate	Patient admission
damage			when the sample
			was taken
Lymphoma within	Binary	Univariate/multivariate	Patient admission
last 5 years			when the sample
			was taken

	Chemotherapy in	Binary	Univariate/multivariate	Patient admission
	preceding 12 weeks			when the sample
	to index sample			was taken
	Renal replacement	Binary	Univariate/multivariate	Patient admission
	therapy (eg.			when the sample
	Dialysis) within 7			was taken
	days of sample			
	Chronic kidney	Binary	Univariate/multivariate	Patient admission
	disease			when the sample
				was taken
	Radiotherapy in	Binary	Univariate/multivariate	Patient admission
	preceding 12 weeks			when the sample
	to index sample			was taken
	Moderate or severe	Binary	Univariate/multivariate	Patient admission
	liver disease			when the sample
				was taken
	UTI	Binary	Univariate/multivariate	Patient admission
				when the sample
				was taken
	Transplant	Binary	Univariate/multivariate	Patient admission
				when the sample
				was taken
	Other	Binary	Univariate/multivariate	Patient admission
				when the sample
				was taken
5.8	Patient	Categorical	Univariate	Patient admission
	gastrointestinal			when the sample
	symptoms at time			was taken
	of index sample			
5.9	Was there an	Binary	Univariate	Patient admission
	alternative cause			when the sample
	for the patients			was taken
	diarrhoea			
5.9.1	If yes please give	Categorical	Univariate	Patient admission
	details			when the sample
				was taken
5.10	Duration of	Number of	Univariate	Patient admission
	diarrhoea before	days of		when the sample
	and after the index	diarrhoea is		was taken
F 44	sample	Continuous		Detionst e destade
5.11	Did the patient	віпагу	Univariate	Patient admission
	undergo any			when the sample
	diagnostic			was taken
	procedures for this			
	episode of CDI?			
5.11.1	It yes, please	Categorical	Univariate	Patient admission
	complete the table			when the sample

				was taken
5.12	Evidence of colitis	Binary	Univariate	Patient admission
				when the sample
				was taken
5.12.1	If yes please give	Categorical	Univariate	Patient admission
	details			when the sample
				was taken
5.13	Was the patient in	Binary	Univariate	Patient admission
	contact with a			when the sample
	diagnosed			was taken
	Clostridium difficile			
	case in the			
	preceding 3 months			
E 12 1		Catagorical	Univariato	Dationt admission
5.15.1	the date	Categorical	Univariate	when the sample
				was taken
5.14	Was the patient in	Binary	Univariate	Patient admission
	kissing contact of	Dinidi y	omratice	when the sample
	an infant in the			was taken
	preceding 3 months			
	to the sample?			
5.14.1	If yes please give	Categorical	Univariate	Patient admission
	the date			when the sample
				was taken
5.15	Did the patient	Binary	Univariate	Patient admission
	receive mechanical			when the sample
	ventilation			was taken
5.15.1	If yes, please give	Continuous	Univariate	Patient admission
	une duration of the			when the sample
	minutes			was taken
5.16	Was the patient	Binary	Univariate	Patient admission
	source isolated due			when the sample
	to CDI			was taken
5.16.1	If yes, please give	Continuous	Univariate	Patient admission
	the duration of			when the sample
	source isolation in			was taken
	days			
5.16.2	Did the patient in	Binary	Univariate	Patient admission
	source isolation			when the sample
	lead to the blocking			was taken
- 10 -	of beds			
5.16.3	If yes, how many	Continuous	Univariate	Patient admission
	beas were blocked			when the sample
6 Dave 11	uuring that time?			was taken
6. Drug H	istory			

6.1	Was the patient prescribed	Binary	Univariate/multivariate	Patient admission when the sample was taken
	at the time or after			was taken
6.1.1	If Yes please complete table	Class of antibiotic is Categorical	Univariate/multivariate	Patient admission when the sample was taken
		Number of dates of		
		Continuous	Univariate/multivariate	
		Indication is Categorical	Univariate/multivariate	
		Route is Categorical		
6.2	Was the patient prescribed antibiotics for an infection other than CDI (or for prophylaxis) in the 12 weeks preceding the index sample	Binary	Univariate/multivariate	Up to 12 weeks previous to the sample
6.2.1	If Yes please complete table	Class of antibiotic is Categorical	Univariate/multivariate	Up to 12 weeks previous to the sample
		Number of	Univariate/multivariate	
		treatment is Continuous	Univariate/multivariate	
		Indication is	Univariate/multivariate	
		Categorical		
		Route is Categorical		
6.3	Did the patient have proton pump inhibitors in the 12 weeks preceding the index sample	Binary	Univariate/multivariate	Up to 12 weeks previous to the sample
6.3.1	If yes please	Name of PPI	Univariate/multivariate	Up to 12 weeks

r				
	complete the table	is Categorical	Univariate/multivariate	previous to the sample
		Number of dates of	Univariate/multivariate	
		Continuous	Univariate/multivariate	
		Indication is Categorical		
		Route is Categorical		
6.4	Has the patient had any drugs which affect the gastrointestinal tract in the 12 weeks preceding the index sample	Binary	Univariate/multivariate	Up to 12 weeks previous to the sample
6.4.1	If yes please complete the table	Name of drug is Categorical	Univariate/multivariate Univariate/multivariate	Up to 12 weeks previous to the sample
		Number of dates of treatment is Continuous	Univariate/multivariate Univariate/multivariate	
		Indication is Categorical		
		Categorical		
6.5	Has the patient had systemic steroids or other systemic immunosuppressive drugs in the 12 weeks preceding the index sample	Binary	Univariate/multivariate	Up to 12 weeks previous to the sample
6.5.1	If yes please complete the table	Name of drug is Categorical	Univariate/multivariate Univariate/multivariate	Up to 12 weeks previous to the sample
		Number of dates of	Univariate/multivariate	

		treatment is		
		Continuous	Univariate/multivariate	
		Indication is		
		Categorical		
		Route is		
		Categorical		
7. CDI trea	Did the nation	Binary	Univariate/multivariate	Patient admission
/.1	require	Dinary		when the sample
	change/escalation			was taken
	of CDI medication			
7.1.1	If yes please	Name of	Univariate/multivariate	Patient admission
	complete the table	drug is		when the sample
	below	Categorical	Univariate/multivariate	was taken
		Number of		
		dates of	Univariate/multivariate	
		treatment is		
		Continuous	Univariate/multivariate	
		Indication is		
		Categorical		
		Route is		
		Categorical		
7.2	Did the patient	Binary	Univariate/multivariate	Patient admission
	require			when the sample
	change/escalation			was taken
	of surgical			
7.2.1	If ves please	Name of	Univariate/multivariate	Patient admission
	complete the table	drug is		when the sample
		Categorical	Univariate/multivariate	was taken
		Number of		
		dates of	Univariate/multivariate	
		Continuous	Univariate/multivariate	
		Continuous		
		Indication is		
		Categorical		
		Route is		
0.6		Categorical		
8. Surgery				

8.1	Has the patient had	Binary	Univariate/multivariate	Up to 12 weeks
	12 wooks proceeding			previous to the
	12 weeks preceding			sample
011		Dinorry		Un to 12 weaks
8.1.1	If yes was it Elective	Віпагу	Univariate/multivariate	Up to 12 weeks
	or Acute			previous to the
0.1.0				sample
8.1.2	Please complete	Type of .	Univariate/multivariate	Up to 12 weeks
	table	surgery is		previous to the
		Categorical	Univariate/multivariate	sample
		Number		
		Number of		
		days		
		between		
		surgery and		
		sample is		
		Continuous		
9. GI Inter	ventions			
9.1	Has the patient had	Binary	Univariate/multivariate	Up to 12 weeks
	any Gi			previous to the
	Interventions or			sample
	diagnoses in the 12			
	weeks preceding			
	the index sample			
9.1.1	If yes please	Туре от	Univariate/multivariate	Up to 12 weeks
	complete the table	intervention		previous to the
		IS Colored in al		sample
		Categorical	Univariate/multivariate	
		Number of		
		Number of		
		uays		
		between		
		intervention		
		Continuous		
10 Outcor	nes	continuous		
If the sample was taken as a hernital				
inpatient		pical		
10.1	During the 30 davs	Binarv	Univariate/multivariate	Up to 30 davs
	after the sample	, ,	,	after the index
	was the patient.			sample
	was the patient	Continuous	Univariate/multivariate	· · · ·
	discharged	(no. of		
		davs)		
10.2	Was the patient re-	Binarv	Univariate/multivariate	Up to 30 days
	admitted	,		after the index

				sample		
10.2.1	If yes, please give	Continuous	Univariate/multivariate	Up to 30 days		
	the dates of	(no. of		after the index		
	subsequent	days)		sample		
	hospital admissions					
10.3	If the sample was	Binary	Univariate/multivariate	Up to six months		
	taken as a hospital	-		after the index		
	inpatient, was the			sample		
	patient discharged	Continuous	Univariate/multivariate			
	>30 days after the	(no. of				
	sample	days)				
If the sam	ple was taken as a con	nmunity				
patient	•	-				
10.4	Was the patient	Binary	Univariate/multivariate	Up to 30 days		
	admitted to			after the index		
	hospital			sample		
10.4.1	If yes, please give	Continuous	Univariate/multivariate	Up to 30 days		
	dates of the	(no. of		after the index		
	subsequent	days)		sample		
	hospital admissions					
If the sam	If the sample was taken as a hospital inpatient or a community patient					
10.5	Did the patient die	Binary	Univariate/multivariate	Up to 30 days		
	in the 30 days after			after the index		
	the sample			sample		
		Continuous	Univariate/multivariate			
		(no. of				
		days)				
10.5.1	If yes, was the	Binary	Univariate/multivariate	Up to 30 days		
	death linked to CDI			after the index		
				sample		
10.6	Was the patient	Binary	Univariate/multivariate	Up to six months		
	admitted to			after the index		
	hospital between			sample		
	30 days and 6					
	months after the					
	sample					
10.6.1	If yes, please give	Continuous	Univariate/multivariate	Up to six months		
	the dates of	(no. of		after the index		
	hospital admissions	days)		sample		
10.7	Did the patient die	Binary	Univariate/multivariate	Up to six months		
	between 30 days			after the index		
	and 6 months after			sample		
	sample?	Continuous	Univariate/multivariate			
		(no. of				
		days)				
10.7.1	If yes, was the	Binary	Univariate/multivariate	Up to six months		
	death linked to CDI			after the index		

		sample

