#### 3.3.6 Data collection

Data will be collected via a standardised CRF, with a full supporting SOP. The CRF will be completed by the clinical care team at the participating site that submitted the sample (during O1.1). The CRF will not contain any participant identifiable data; all data will be held against a pseudoanonymised study code, with the link back held by the clinical care team only. COMBACTE-CDI investigators will not access participant's notes or access the link back. Once the CRF data has been collected and validated and verified the link-back will be destroyed by the local study site.

Data will be collected on the following variables to examine risk factors for CDI;

- Prior treatment with cytotoxic drugs
- Prior treatment with PPIs
- Underlying diagnoses
- Co-morbidities
- Previous antibiotics (preceding 12 weeks)
- Previous hospitalisation (preceding 12 weeks)
- Admission history (if an in-patient)
- Residential status (if in the community), e.g. home/nursing home
- Previous CDI
- Kissing contact with an infant
- Known contact with CDI case
- Previous wards/movement within hospital

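### SAP Appendix 1 item 2.2 counts ward moves made after the stool sample, so moves that follow CDI could enter the risk-factor regression as exposures

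*SAP*

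**What the plan says.** Protocol 3.3.6 includes "Previous wards/movement within hospital" among the risk-factor variables.

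SAP Appendix 1 collects this as item 2.2, "Did the patient move wards during their admission", with the time window "Patient admission when the sample was taken" and the analysis type univariate/multivariate. Item 2.2.1 records the timing of moves ("Number of days between admission and movement is" continuous), and item 2.1.1 records the timing of the sample ("Number of days between admission and index sample is Continuous"). Neither item says that moves after the sample are set aside.

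Other exposures in the table do carry a limit. Healthcare contact is "Up to 6 months previous to sample", and prior antibiotics, PPIs, surgery and GI interventions are restricted to the 12 weeks before it. Item 5.16 separately records whether the patient was "source isolated due" to CDI.

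SAP 7.3 enters every variable from the univariate analysis in an unconditional logistic regression with case/control status as the dependent variable. It uses forward selection and ranks risk factors from the selection process.

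In item 5.7, cardiac arrest and renal replacement therapy are defined as "within 7 days of" the sample, with no direction. Pneumonia and UTI have no limit in the item text.

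**The concern.** In a case-control analysis of risk factors, exposure has to precede the index date, which SAP 6.3 sets at stool sample collection. Item 2.2 runs past that date to the end of the admission. SAP 6.3 also confirms that the CRF covers the six months after the sample, so later moves will be on the form.

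Some later moves may be a result of CDI: item 5.16 shows that isolation because of CDI is expected. A transfer made for that reason would be coded as moved, exactly like a transfer that preceded infection. A longer stay after the sample also gives more opportunity to move. If either applies more to cases than to controls, the odds ratio for ward movement rises with no causal effect, and the variable may be selected and ranked. Risk factors for CDI are one of the two main analysis objectives in SAP 2.5.

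**Working it through.** **Reading the items.** The wording of item 2.2 covers the whole admission. No rule in SAP 7.2, 7.3 or Appendix 1 narrows it. Items 2.1.1 and 2.2.1 both count days from admission, so each move can be placed before or after the sample. What is missing is an analysis rule; the data are there.

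**Illustration.** The plan states no figure for ward moves, so there is none to reproduce. All movement rates below are assumptions. Let *a* be the proportion moving before the sample, the same in both groups (true odds ratio 1). Let *q* be the proportion of the rest who move afterwards.

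Observed proportion moved: *p* = *a* + (1 − *a*)*q*. Apparent OR = [*p*₁/(1 − *p*₁)] / [*p*₀/(1 − *p*₀)], with 1 for cases and 0 for controls.

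Take *q* as 15-40% in cases and 5-10% in controls. The extremes come from pairing the lowest case rate with the highest control rate, and the reverse:

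| *a* | *q* cases | *q* controls | *p*₁ | *p*₀ | OR |
|---|---|---|---|---|---|
| 0.30 | 0.15 | 0.10 | 0.405 | 0.370 | 1.16 |
| 0.30 | 0.40 | 0.05 | 0.580 | 0.335 | 2.74 |
| 0.40 | 0.15 | 0.10 | 0.490 | 0.460 | 1.13 |
| 0.20 | 0.40 | 0.05 | 0.520 | 0.240 | 3.43 |
| 0.30 | 0.20 | 0.20 | 0.440 | 0.440 | 1.00 |

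First row in full: 0.30 + 0.70 × 0.15 = 0.405 and 0.30 + 0.70 × 0.10 = 0.370; (0.405/0.595)/(0.370/0.630) = 0.681/0.587 = 1.16.

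So the range is 1.16 to 2.74 at *a* = 30%, and 1.13 to 3.43 over *a* = 20-40%.

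**Would it be detected as an effect?** SAP Table 1 has 83 + 49 + 24 = 156 hospital cases and 365 hospital controls. For an unadjusted two-sided 5% comparison of proportions:

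- *a* = 20%, *q* = 20% v 5%: observed 36% v 24%, OR 1.78. The pooled proportion is (156 × 0.36 + 365 × 0.24)/521 = 0.276. The standard error is 0.0428 under no difference and 0.0445 under the observed rates. Then z = (0.12 − 1.96 × 0.0428)/0.0445 = 0.81, about a 79% chance of p < 0.05.
- *a* = 40%, *q* = 10% v 5%: observed 46% v 43%, OR 1.13, about a 9% chance.

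**After the change.** If only moves before the sample count, *p* = *a* in both groups and the OR is 1.00 in every row.

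**The case against.** The case against rests on five points.

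- **The bias needs a difference between groups, and the documents give no rates.** This stands. Controls also had unformed stool (protocol 3.1.3), so they may be moved on suspicion too. Central results are not returned to sites (protocol 5.0), so isolation follows local diagnosis or suspicion only. Of the 156 hospital cases, 49 + 24 = 73 are CCNA negative. Isolation need not involve a change of ward. A reader might infer that ward movement is bound to emerge as a false risk factor; the documents support only that it could.
- **The time-window column is a loose label.** This also stands. The same admission window is attached to age, gender and chemotherapy in the 12 weeks before the sample. It is weak evidence on pneumonia and UTI. For ward moves the point does not depend on it, because the item's own wording covers the admission.
- **In the protocol phrase, the word for earlier may qualify only the wards and not the movement.** That reading is possible. It does not help the SAP, since a risk factor must still precede the index date.
- **The timing is already collected, and days to sample is already a regression candidate.** True, and it makes the remedy cheap. But forward selection may drop days to sample, and adjusting for it would not remove post-sample moves from item 2.2.
- **The acute events are a different matter.** Largely right. A reader might infer that all are counted over the whole admission and are exposures named in the protocol. Cardiac arrest and renal replacement are bounded to 7 days, and protocol 3.3.6 lists only underlying diagnoses and co-morbidities in general terms.

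A reader might also infer that the transmission model would take post-sample moves as a route of acquisition. Protocol 3.4.7 names the risk-factor analysis as an input but does not say how ward movement would be used.

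**Conclusion.** The point holds for ward movement. As written, item 2.2 mixes moves before and after the index sample and goes into the risk-factor regression in that form. The result could be a spurious association, upward if cases are moved after the sample more often than controls.

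The size is unknown. The odds ratios of 1.16 to 2.74, or 1.13 to 3.43 over the wider range, are illustrations. They assume no true effect, equal movement before the sample, and a higher post-sample rate in cases throughout. Under equal post-sample rates there is no distortion in this setting.

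The acute events in item 5.7 are a secondary point about unstated direction or onset. The change should be made before the analysis, because it is inexpensive and bears on a main objective.

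**What to change.** In SAP Appendix 1:

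1. For the risk-factor analysis, derive ward movement as moves before the index sample only: days to movement (2.2.1) less than days to sample (2.1.1). A move on the sample day then counts as later, which the SAP should say.
2. Keep days from admission to sample (2.1.1) in that model whatever forward selection does, since a longer stay before the sample gives more opportunity to move.
3. Report moves after the sample descriptively.
4. In item 5.7, count cardiac arrest only if dated before the sample. Leave pneumonia, UTI and renal replacement out of the risk-factor regression where onset before the sample cannot be established.

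The cost is one derived variable and some SAP wording, with no new data collection. Cardiac arrest has a date item; pneumonia, UTI and renal replacement do not, so those three may drop out of the regression.
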